2. TRIAL OBJECTIVES

Trial Objectives: The primary objective of this trial is to:

- To evaluate the sensitivity and specificity of 2D and 4D contrast enhanced ultrasound for monitoring transarterial chemoembolization (TACE) response 1-2 weeks and 1 month post treatment as an alternative to contrast-enhanced magnetic resonance (MRI) or computed tomography (CT) imaging

The secondary aim of this trial is to:

- To develop quantitative biomarkers based on the ultrasound contrast agent kinetics for identifying patients requiring retreatment of residual disease.

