Quantitative analysis of 2D and 4D CEUS datasets will be performed off-line using Matlab (Mathworks, Natick, MA). Motion compensation will first be performed using modified approaches of either a kernel matching [Dave et al. 2009] or a dual mode registration [Bouhleb et al. 2014] motion compensation technique. Parametric images of both the mass and surrounding liver tissue will be generated using 2D [Eisenbrey et al. 2011b] and 4D [Sridharan et al. 2014] algorithms previously developed by our lab to quantify maximum intensity, perfusion, time to peak, and area under the time intensity curve. Based on images or volumes from the arterial wash-in phase, images will be cropped to include the tumor and margins of 20% of the mass diameter. Vascular skeletonization of the mass and surrounding margins will then be performed [Eisenbrey et al. 2011c] and fractal dimensionality of the skeletonized images calculated (another potential quantifiable indicator of malignancy [Taverna et al. 2009]). Differences in all quantified parameters between pre- and post- treatment will then be calculated and compared between groups to determine if significant biomarkers exist in identifying patients in need of re-treatment.

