7.2 Statistical Analyses

Data analysis from this multi-center clinical trial will be performed to characterize 2D and 4D CEUS as a follow-up imaging tool for the evaluation of residual tumoral blood flow in patients with HCC treated with TACE.

Our statistical analysis will address three major questions:

1. Does 2D and 4D CEUS 1-2 weeks post TACE yield sensitivity and specificity greater than 90% for identifying residual tumor blood flow, thereby providing reliable earlier identification (relative to the current clinical standard) of patients in need of retreatment?
2. Does 2D and 4D CEUS 1 month post TACE yield sensitivity and specificity greater than 90% for identifying residual tumor blood flow, thereby providing an accurate, safe, and cost-effective imaging alternative for identifying TACE patients in need of retreatment?
3. Are quantifiable biomarkers generated by parametric imaging of 2D and 4D CEUS exams able to differentiate between fully treated and incompletely treated masses by measuring blood flow kinetics?

The first three cases at each institution will be used as reader training cases and will not be included in the final analysis. In the event of all cases showing identical response (i.e. all incompletely or completely treated), the first case with an alternative outcome will be substituted for the 9th case. Following reader training, each reader (all of whom have previous experience with CEUS and volumetric ultrasound) will be asked to evaluate all 201 remaining cases. 2D and 4D CEUS exams will be read separately and only after randomization. 2D cases will be viewed in a standard DICOM viewer, while 4D cases will be viewed in GE's 4D View software. Readers will first be asked to review both the patient's baseline CE-MRI/CT and CEUS exams to identify the size and location of the treated mass. Following baseline review, each reader will review the 1-2 week and 1 month CEUS exam (in random order). Intratumoral blood flow will be assessed as present or not present. Readers will then be asked to interpret the patient's 1 month follow-up CE-MRI/CT images and again evaluate the need to retreat based on residual blood flow. Finally, when available, readers will review subsequent CE-MRI/CT imaging studies (up to six months post TACE). MRI/CT evaluations will be based on mRECIST criteria. All imaging studies will be read twice by each

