reader. Studies will be presented in random order. The second round reads will be performed at least one month after the first. Outcomes will be defined as incompletely treated (i.e. requiring retreatment) based on (in order of preference of reference standard): a) pathological examination of explanted livers demonstrating live tumors; b) tumor enhancement seen with CT or MR and confirmed via angiography during retreatment; c) tumor growth on 6 month follow-up CE-CT/MRI; or d) asymmetrical or nodular tumor enhancement on CE-MRI/CT on 6 month follow-up. Incomplete treatment on CEUS (2D or 4D) will be evaluated by each reader and evidenced by the tumor showing either residual blood flow after treatment or nodular peripheral blood flow.

For questions 1-2, sensitivity (the ability to detect patients in need of retreatment) and specificity (the ability to identify patients who do not require retreatment) will first be calculated on a reader by reader basis. Four 2 x 2 tables will be constructed comparing the need for re-treatment based on the clinical gold standard described above and CEUS, tabulating true positives, false positives, false negatives, and true negatives. A table will be created for CEUS at 1-2 weeks and 1 month for both 2D and 4D CEUS and used to calculate sensitivity, specificity, accuracy, positive predictive value, and negative predictive value. Statistical significance between the reference standard and each of the 4 CEUS groups will be determined using a McNemar test. These values will also be calculated based on the majority decision (i.e. 4 or more readers in agreement). In the event of discordant readings during this analysis, tumor outcome will be decided by consensus by the two readers at TJU. Differences between techniques (2D vs. 4D) and time points (1-2 weeks vs. 1 month post treatment) will be determined by comparing areas under the receiver operating characteristic curves for each modality/time point based on necessity of tumor retreatment. Intra-rater and inter-rater variability will be calculated using a Shrout and Fleiss Interclass Correlation [Shrout and Fleiss 1979]. Finally, a logistical regression and analysis of variance will be performed to determine if significant variations exist between individual sites (to determine operator dependence), lesion size (tumor size dependency) or between patients treated with cTACE vs. DEB-TACE (treatment dependency).

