For statistical question 3, all quantitative parameters will be compared between fully treated and incompletely treated masses using a Student's t-test. Additionally, lesions that demonstrate lack of residual enhancement at 1 month, but show recurrence at 6 month follow-up, will be compared to completely treated masses to determine if quantitative CEUS parameters can detect this lower level of residual disease. Statistical analysis will be performed with assistance from the biostatistician co-investigator using Stata 12.0 (Stata Corp, College Station, TX) with p values < 0.05 considered statistically significant after a Bonferroni-type adjustment for multiple tests. These statistical tests will answer our three major questions regarding the sensitivity and specificity of 2D and 4D CEUS as an imaging tool for the follow-up of TACE

at 1-2 weeks and 1 month (specific aims 1-2), as well as the influence of operator, reader, tumor size, and embolization material.

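### No accuracy measure is planned for the quantitative CEUS biomarkers: question 3 rests on t-tests of group means, which can be significant at an AUC of only about 0.6

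*Combined protocol and SAP*

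**What the plan says.** Section 2 gives the secondary aim: "To develop quantitative biomarkers based on the ultrasound contrast agent kinetics for identifying patients requiring retreatment of residual disease". Section 7.2 makes this the third of three major questions and asks whether the biomarkers are "able to differentiate between fully treated and incompletely treated masses by measuring blood flow kinetics".

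The method for question 3, also in Section 7.2, is that "all quantitative parameters will be compared between fully treated and incompletely treated masses using a Student's t-test". Significance there means "p values < 0.05 considered statistically significant after a Bonferroni-type adjustment for multiple tests"; the number of tests in the family is not given. Section 6.5 adds that "Differences in all quantified parameters between pre- and post- treatment will then be calculated and compared between groups", the purpose being "to determine if significant biomarkers exist in identifying patients in need of re-treatment".

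A second comparison concerns lesions without enhancement at 1 month that recur by 6 months. These "will be compared to completely treated masses to determine if quantitative CEUS parameters can detect this lower level of residual disease". No test or accuracy measure is named for it.

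Section 7.2 does plan an ROC analysis, "comparing areas under the receiver operating characteristic curves for each modality/time point based on necessity of tumor retreatment", but in the paragraph for questions 1-2, to compare 2D with 4D and one time point with the other. The logistic regression in that paragraph addresses site, lesion size and type of TACE.

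**The concern.** The aim and the question are about classification: can a parameter value sort a given mass into the right group? A t-test answers a different question, whether the two group means differ by more than chance. With about 200 masses, means can differ clearly while the two distributions overlap almost completely.

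Questions 1-2 are held to sensitivity and specificity above 90%. Question 3 serves the same retreatment decision but has no accuracy criterion, and statistical significance is the nearest thing to one. A parameter could therefore be reported as a significant biomarker without any evidence on how often it would be right. If cut-offs were later chosen on the same data, across many parameters and without a planned correction for optimism, the reported performance would tend to be too good.

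**Working it through.** **1. The plan's own figures.** Section 7.2.1 powers aims 1-2 only, with an exact binomial test of 0.98 against 0.90. At one-sided alpha 0.05:
- n = 133: reject at 126 or more correct; actual alpha 0.0385, power 0.9945.
- n = 67: reject at 65 or more correct; actual alpha 0.0307, power 0.8494.

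Both match the table. No effect size or power is given for question 3.

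**2. Group sizes.** Section 7.2.1 analyses 201 patients at a prevalence of 66.7%. It states both 135 and 133 needing retreatment, and 0.667 x 201 = 134. I use 134 and 67. The splits 135/66 and 133/68 change the AUCs below by at most 0.001.

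**3. Number of tests (assumed).** Section 6.5 lists maximum intensity, perfusion, time to peak, area under the time-intensity curve and fractal dimension: 5 parameters x 2 modalities x 2 time points = 20 tests. I also show 1 and 40.

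**4. Smallest observed standardised difference that is significant** (two-sided, 199 degrees of freedom):

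d = t x sqrt(1/134 + 1/67) = t x 0.1496

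**5. Conversion to discrimination,** assuming normal distributions with equal variance:
- AUC = Phi(d / sqrt 2)
- sensitivity = specificity at the midpoint cut = Phi(d / 2)
- specificity at 90% sensitivity = Phi(d - 1.2816)

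| Tests in family | t | d | AUC | Sens = spec at midpoint | Spec at 90% sens |
|---|---|---|---|---|---|
| 1 (unadjusted) | 1.972 | 0.295 | 0.583 | 56% | 16% |
| 20 | 3.062 | 0.458 | 0.627 | 59% | 21% |
| 40 | 3.274 | 0.490 | 0.635 | 60% | 21% |

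**6. What the 20-test row means for decisions.** At 90% sensitivity the specificity is 0.205.
- False positives: 67 x (1 - 0.205) = 53 of 67 fully treated masses.
- True positives: 0.90 x 134 = 120.6. PPV = 120.6 / (120.6 + 53.3) = 69%, against a prevalence of 66.7%.
- NPV = 13.7 / (13.7 + 13.4) = 51%, so about half of the test-negative masses would still need retreatment.

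**7. Two reference points.**
- A true d of 0.585 has 80% power at 20 tests. It corresponds to an AUC of 0.660, with sensitivity and specificity of 61.5% at the midpoint.
- To have 90% sensitivity and 90% specificity together, d must be 2 x 1.2816 = 2.56 (AUC 0.965).

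**8. Fewer evaluable masses (assumed).** With 80 and 40 masses, the AUC at the significance threshold is 0.607 unadjusted and 0.664 for 20 tests.

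**The case against.** The aim is secondary and worded as development. Section 7.2.1 calls aims 1-2 the most clinically important, and a Bonferroni-adjusted comparison of groups is a recognised first screen for candidate markers; cut-offs and validation can follow later. This stands as a reason to keep the t-tests and to treat the point as an improvement to a secondary analysis. It does not remove the gap, because Section 7.2 presents its tests as the answer to all three major questions. Bonferroni controls false positives; it does not measure discrimination.

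Three stronger readings are tempting, and the documents do not support them.

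- A reader might infer that these parameters will discriminate poorly. The figures above are the least that significance guarantees. Residual flow against no flow could give a far larger difference.
- A reader might infer that a significant t-test would formally count as meeting the secondary aim. The plan has no such rule; the phrase in Section 6.5 about significant biomarkers is the nearest wording.
- A reader might infer from Section 6.5 that the t-tests are confined to change scores and so waste precision compared with adjusting for baseline. Section 7.2 does not restrict the t-test to differences. The usual precision argument needs equal baseline means and equal pre- and post-treatment standard deviations. The groups here are defined by outcome, and the treatment aims to abolish flow, so neither can be taken for granted. The documents give no pre-post correlation either.

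**Conclusion.** The concern holds as a gap between question and method. The plan asks whether parameters can classify masses and provides only a comparison of means. Neither the ROC analysis for questions 1-2, nor the logistic regression, nor the late-recurrence comparison fills that gap.

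Significance alone guarantees an observed AUC of only about 0.58 (unadjusted) to 0.64 (40 tests), with 0.63 for the assumed family of 20. This rests on two-sided tests, normal parameters with equal variance, one mass per patient and complete follow-up. The last two are idealised: the Synopsis allows up to two lesions per patient to be imaged, and Section 3.1 allows for a missed early exam. Fewer masses raise the floor somewhat, to an AUC of 0.66 for 80 and 40 masses at 20 tests, still far from the level that questions 1-2 require. The primary sensitivity and specificity analyses are not affected.

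**What to change.** Add to the question 3 paragraph of Section 7.2:

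- For each parameter, modality and time point, report the ROC AUC against the reference standard with a 95% confidence interval that allows for patients with two lesions (for example, a bootstrap that resamples patients).
- For any chosen cut-off or combination of parameters, report sensitivity and specificity with internal validation by bootstrap or cross-validation, repeating the selection step within each resample.
- Name the same accuracy measure for the late-recurrence comparison.
- Keep the Bonferroni-adjusted t-tests as a descriptive screen and state the number of tests in the family.

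The parameters and outcomes are already collected, so the cost is a little more analysis. The downside is that AUCs with intervals and validated performance will look less flattering than p-values.

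### Question 3 asks whether quantitative CEUS parameters can discriminate fully from incompletely treated masses, but its only named test compares group means and no measure of discrimination is planned.

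*Combined protocol and SAP*

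**What the plan says.** Section 2 gives the secondary aim: "To develop quantitative biomarkers based on the ultrasound contrast agent kinetics for identifying patients requiring retreatment of residual disease". Section 7.2 turns this into question 3, which asks whether the biomarkers are "able to differentiate between fully treated and incompletely treated masses by measuring blood flow kinetics". Section 6.5 says that pre- to post-treatment differences will be "compared between groups to determine if significant biomarkers exist in identifying patients in need of re-treatment".

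The analysis for question 3 is in section 7.2 and is repeated in the synopsis: "all quantitative parameters will be compared between fully treated and incompletely treated masses using a Student's t-test". A second comparison takes lesions that look clear at 1 month but recur by 6 months. These "will be compared to completely treated masses to determine if quantitative CEUS parameters can detect this lower level of residual disease", and no test is named for that comparison. The significance rule is "p values < 0.05 considered statistically significant after a Bonferroni-type adjustment for multiple tests", and the number of tests is not given. Section 7.2 then presents these tests as the answer to all three questions.

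ROC areas, sensitivity, specificity and predictive values appear only in the paragraph for questions 1-2. There they concern the readers' CEUS assessments and the comparisons of 2D with 4D and of the two time points.

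**The concern.** The aim and the question are about classification: can a parameter separate masses, and can it pick out the patients who need retreatment? The null hypothesis of the named test is that the two group means are equal. With about 200 masses that null can be rejected when the two distributions still overlap heavily. Sections 6.5 and 7.2 give no criterion other than significance, so a significant p value is the natural basis for answering yes to question 3.

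At stake is what the secondary aim delivers. The trial could report biomarkers that separate patients poorly, with no cut-off and no error rates for a later study to build on. The 6-month recurrence comparison is worse specified: it asks whether the parameters can detect residual disease, and it names neither a test nor an accuracy measure.

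**Working it through.** **Inputs from the documents**
- Analysis set (section 7.2.1): 201 patients, 135 needing retreatment, so 201 - 135 = 66 fully treated. The next sentence says 133 with disease. Using 133/68 or 134/67 changes the powers below by about one percentage point or less.
- Parameters (section 6.5): four are named ("quantify maximum intensity, perfusion, time to peak, and area under the time intensity curve"), plus "fractal dimensionality of the skeletonized images calculated", making 5.
- Alpha: 0.05 after a Bonferroni-type adjustment, divisor *k* not stated.

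**Assumptions**
- Two-sided t-test, normal markers with equal SD, one mass per patient, complete data.
- *k* from 1 to 40. For orientation: 5 parameters; 5 x 2 modes = 10; 10 x 2 post-treatment time points = 20; doubled again = 40.

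**The plan's own figure first.** The plan gives no power for question 3; section 7.2.1 covers aims 1-2 only. Those figures reproduce with an exact one-sided binomial test at 0.05, null 0.90 and alternative 0.98:
- n = 133: reject at 126 or more; actual alpha 0.0385; power 0.9945.
- n = 67: reject at 65 or more; actual alpha 0.0307; power 0.8494.

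Both match the table row for N = 200.

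**From ROC area to standardised difference.** Under the model, d = sqrt(2) x z(AUC), where z is the standard normal quantile.
- AUC 0.65: d = 0.545.
- AUC 0.70: d = 0.742.

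**What such markers can do**
- Equal-error cut-off, sensitivity = specificity = Phi(d/2): 0.607 at AUC 0.65 and 0.645 at AUC 0.70.
- Sensitivity at 90% specificity = Phi(d - 1.2816): 0.231 and 0.295.

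**Power of the t-test.** The noncentrality is d / sqrt(1/66 + 1/135) = d / 0.1502, which is 3.63 at AUC 0.65 and 4.94 at AUC 0.70. With 199 degrees of freedom and alpha = 0.05/*k*, the noncentral t gives:

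| *k* | AUC 0.65 | AUC 0.70 |
|---|---|---|
| 1 (unadjusted) | 95.1% | 99.8% |
| 5 | 84.7% | 99.0% |
| 10 | 78.4% | 98.1% |
| 20 | 71.3% | 96.8% |
| 40 | 63.8% | 95.0% |

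**Sensitivity to missing data.** If 80% of cases are usable (assumed: 108 versus 53) and *k* = 20, the powers are 57% and 91%.

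**Smallest observed effect that reaches significance.** d = t_crit x 0.1502. For *k* = 1 this is 1.972 x 0.1502 = 0.296, or AUC 0.58. For *k* = 40 it is 3.274 x 0.1502 = 0.492, or AUC 0.64.

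**The case against.** Question 3 serves a secondary aim of biomarker development, and the trial is sized on aims 1-2 alone. Screening parameters for group differences is a usual first step. No section says that a significant parameter will guide retreatment, so treating significance as a yes is an inference. That is fair and limits the weight of the point. The inference is still reasonable: section 6.5 speaks of finding significant biomarkers, section 7.2 says the tests will answer the three questions, and no other criterion is offered.

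Three stronger readings are tempting, and the documents do not support them.
- **Any marker with ROC area 0.65-0.70 would almost always be significant.** At 0.65 that needs an unadjusted test (95%), and the plan adjusts. Missing data lower the figure further: section 3.1 allows for a missed early exam, and the change scores in section 6.5 need both exams to be analysable.
- **Such markers misclassify a third or more of patients.** This holds at the equal-error cut-off (39% and 36%). At the cut-off that minimises total error with 135 of 201 needing retreatment, the error is 32% and 30%. That is little better than calling every mass incompletely treated, which errs in 66/201 = 33%. The markers are weak either way, but the cut-off has to be stated.
- **The markers fail the trial's 90%/90% standard.** Section 7.2 sets that standard for questions 1-2 only. Under this model it would need a ROC area of about 0.965, but the plan sets no accuracy bar for question 3.

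**Conclusion.** The point holds as a mismatch between question and analysis. The only named test for question 3 cannot show discrimination, and nothing elsewhere in the plan supplies a measure of it for the quantitative parameters. After adjustment over 5 to 40 tests, a weak marker with ROC area 0.70 would nearly always be significant (about 95-99% of trials). One with ROC area 0.65 would be significant more often than not (about 64-85%). These figures rest on the assumed divisor, equal-variance normal markers, one mass per patient, a 135/66 split and complete data. The mismatch itself rests on the text and does not depend on them.

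The primary objective and the sample size are unaffected. The change should be made because it is cheap and the secondary aim is not answered without it.

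**What to change.** In section 7.2 and the synopsis:
- Make the question 3 analysis the ROC area of each quantitative parameter, by mode (2D, 4D) and time point, against the same reference standard as questions 1-2, with a 95% confidence interval. Report sensitivity at a specificity stated in advance.
- Base the answer to question 3 on the ROC area and its interval, not on the t-test p value alone. Keep the t-test as a supporting group comparison.
- Name the analysis for the 6-month recurrence comparison; the same ROC approach would serve.
- State how many tests the Bonferroni-type adjustment covers.
- If a cut-off is derived, report its accuracy with cross-validation. A formal success threshold or validation by site is optional for a development aim.

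The interval would be informative at this size: with 135 and 66 masses the Hanley-McNeil standard error is about 0.037 at a ROC area of 0.70, giving roughly 0.63 to 0.77.

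The cost is SAP wording and a small amount of extra analysis, with no new data. The downside is that fewer parameters may be described as useful.

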1.2 Rationale

Successful TACE of a tumor using drug eluting beads is expected to completely obstruct the tumor blood supply. Thus, the fundamental theory behind this study is that CEUS, which uses a blood pooling agent for contrast, will provide a good indicator of the degree of occlusion. If CEUS at one month correlates with the current clinical standard of a contrast-enhanced MRI, this alternative will lead to substantial cost savings. If CEUS at one to two weeks correlates with the current clinical standard of a contrast-enhanced MRI at one month, this will reduce time to retreatment, potentially improving patient outcomes.

We propose a clinical trial to determine the accuracy of using CEUS for the evaluation of TACE of HCC. The purpose of this study is to compare ultrasound derived vascularity and blood flow measurements at varying time intervals to both the clinical evaluation standard and patient outcomes.

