0.9791	0.7135	107							
160	0.9000	0.9800	0.9000	0.9800	0.0500	0.0374	0.0259	0.6670	
0.9735	0.6839	113							
170	0.9000	0.9800	0.9000	0.9800	0.0500	0.0255	0.0181	0.6670	
0.9893	0.6619	120							
180	0.9000	0.9800	0.9000	0.9800	0.0500	0.0382	0.0138	0.6670	
0.9857	0.8879	127							
190	0.9000	0.9800	0.9000	0.9800	0.0500	0.0250	0.0421	0.6670	
0.9945	0.8494	133							
200	0.9000	0.9800	0.9000	0.9800	0.0500	0.0385	0.0307	0.6670	

A total of 201 patients will be used in the final analysis for this study (the first 9 will be used as training cases and excluded), of which 135 (66.7%) will require retreatment. A total sample size of 201 (which includes 133 subjects with the disease) achieves 99% power to reject the null hypothesis for sensitivity, and 85% power to reject the null hypothesis for specificity.

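### Question 3 names an equal-variance t-test for groups of about 135 and 66 with no basis for equal variances; Welch's test guards against error in either direction at almost no cost

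*Combined protocol and SAP*

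**What the plan says.** Section 7.2 Statistical Analyses, repeated in the synopsis under Statistical Methodology, states for question 3 that "all quantitative parameters will be compared between fully treated and incompletely treated masses using a Student's t-test". It adds a second comparison: "lesions that demonstrate lack of residual enhancement at 1 month, but show recurrence at 6 month follow-up, will be compared to completely treated masses". No test is named for that one, and no number of such lesions is given. The threshold is "p values < 0.05 considered statistically significant after a Bonferroni-type adjustment for multiple tests"; the number of tests is not stated.

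Section 6.5 Efficacy Assessments lists the parameters. The algorithms "quantify maximum intensity, perfusion, time to peak, and area under the time intensity curve", and later "fractal dimensionality of the skeletonized images calculated". The same paragraph says that the change in each parameter from before to after treatment is calculated and compared between groups.

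Section 7.2.1 gives the group sizes: "A total of 201 patients will be used in the final analysis for this study", "of which 135 (66.7%) will require retreatment". That leaves 66 fully treated. The sample size rests on aims 1 and 2 alone. Neither section gives an SD, an effect size or a distributional assumption for question 3.

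**The concern.** Student's test estimates one common variance from both groups. With equal group sizes it tolerates unequal spread fairly well. At about 2:1 it does not: the pooled estimate is dominated by the larger group. If the larger group is more variable, the standard error is too big and real differences are missed. If the smaller group is more variable, the standard error is too small and false positives rise.

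The plan gives a reason to doubt equal spread. Section 1.2 says: "Successful TACE of a tumor using drug eluting beads is expected to completely obstruct the tumor blood supply". Values measured after treatment could then be tightly grouped in fully treated masses and widely spread in the others. On the pre-to-post change of section 6.5 the order could reverse, because a mass that loses all its flow has a change as large as its baseline flow and so keeps the full spread between tumors. Either way the pooled assumption is unsupported.

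At stake is the secondary objective, which is also one of the plan's three major statistical questions: a biomarker could be declared on a difference in spread, or a real one missed.

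**Working it through.** **The plan's own figures.** Section 7.2.1 gives power for sensitivity and specificity only. An exact one-sided binomial test at 0.05, null 90% against 98%, gives 0.9945 with 133 diseased (reject at 126 or more) and 0.8494 with 67 non-diseased (reject at 65 or more). These match the stated 99% and 85%. There is no figure for question 3 to reproduce.

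**Inputs from the plan.** 201 analysed and 135 incompletely treated, so 201 − 135 = 66 fully treated. (The section also gives 133 diseased, and 0.667 × 201 = 134.07; the difference is immaterial here.) Five parameters × 2D/4D × two time points = 20 tests, so 0.05/20 = 0.0025.

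**Assumptions.** The 20-test family, two-sided testing, normal data, one mass per patient, the SD ratios, the effect sizes and the late-recurrence counts.

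**Main comparison, closed form.** Let k be the SD of the incompletely treated divided by that of the fully treated (set to 1).

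- Student's SE: √{[(134k² + 65)/199] × (1/135 + 1/66)}
- True SE: √(k²/135 + 1/66)
- R = Student's SE / true SE. Size is about 2Φ(−1.972R) at 0.05. Power for a 4-SE effect at 0.0025 is about Φ(4 − 3.062R).

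For k = 2: Student's SE = √(601/199 × 0.02256) = 0.2610; true SE = √(4/135 + 1/66) = 0.2116; R = 1.233; size about 2Φ(−2.43) = 1.5%; power about Φ(0.22) = 59%.

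For k = 0.5: Student's SE = √(98.5/199 × 0.02256) = 0.1057; true SE = √(0.25/135 + 1/66) = 0.1304; R = 0.810; size about 2Φ(−1.60) = 11%.

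**Main comparison, simulation** (200,000 runs per case; size figures at nominal 5% repeat to within about 0.1 point):

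| SD ratio k | Student size at 5% | Welch size at 5% | Student power, 0.0025, 4 SE | Welch power, 0.0025, 4 SE |
|---|---|---|---|---|
| 0.5 | 11% | 5.0% | not comparable | 81% |
| 0.75 | 7.7% | 5.0% | not comparable | 81% |
| 1 | 5.0% | 5.0% | 82% | 82% |
| 1.5 | 2.6% | 5.0% | 69% | 82% |
| 2 | 1.7% | 5.0% | 59% | 82% |

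Below k = 1, Student rejects more often only because its size is inflated. At nominal 0.0025 and k = 0.5 its size is about 1.45%, roughly six times nominal, so the Bonferroni adjustment does not repair it.

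**Late-recurrence comparison, if Student's test is carried over.** Size at nominal 5% against 66 fully treated masses; the ratio is late-recurrence SD over fully treated SD:

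| Lesions | Ratio 0.5 | Ratio 1 | Ratio 1.25 | Ratio 2 |
|---|---|---|---|---|
| 5 | 0.1% | 5% | 10% | 27% |
| 10 | 0.2% | 5% | 9.6% | 22% |
| 20 | 0.7% | 5% | 8.1% | 16% |

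Welch stays at 4.9–5.8% throughout. At nominal 0.25% it is close to target with 10 or more lesions (0.2–0.4%), but rejects about 0.4–0.7% with 5.

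**The case against.** The best counter-argument is that the direction of error is not established. Section 6.5 compares pre-to-post changes, so grouping of post-treatment values near zero does not carry over. An illustrative model supports this: lognormal baseline flow, with 0–5% remaining in fully treated masses and 5–100% in the others. It gives SD ratios of 1.09, 0.79 and 0.66 for baseline coefficients of variation of 0.3, 0.5 and 0.8. Student's test would then be near nominal or mildly liberal. Time to peak and fractal dimension also need not approach zero when flow stops. All of this stands. It leaves the direction open; it does not make equal variances likely.

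A reader might infer two stronger claims. One is that the main comparison loses more than 20 points of power. That needs an SD ratio of about 1.75–2 or more, the adjusted alpha and a mid-range effect together; at equal SDs nothing is lost. The other is that false positives reach 10–40% in the late-recurrence comparison. That needs the small group to be about 1.25–3 times as variable, and the top of the range needs about 5 lesions and a threefold ratio together. These lesions are selected for showing no enhancement at 1 month, so a spread close to that of fully treated masses is at least as plausible; the same model with 0–15% remaining flow gives a ratio of about 0.95. The plan names no test there in any case. The documents support neither claim as an expected result.

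Finally, question 3 serves the secondary aim and does not drive the sample size. That limits the weight of the point.

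**Conclusion.** The point holds as a weakness in the stated method, with conditional size. For 135 against 66, Student's true size at nominal 5% runs from about 11% to 1.7% as the SD ratio goes from 0.5 to 2. At alpha 0.0025 and a 4-SE effect, the power shortfall against Welch is nil at equal SDs, about 13 points at ratio 1.5 and about 23 at ratio 2. For 5–20 late-recurrence lesions, size under Student's test could be anywhere from under 1% (ratio 0.5) to 16–27% (ratio 2). The SD ratios, lesion counts, effect size and 20-test family are assumptions. What comes from the plan is the named test, the roughly 2:1 split, the missing variance information and the unnamed second test. The power stated for aims 1 and 2 is unchanged.

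**What to change.** In section 7.2 and in the synopsis, replace Student's t-test with Welch's unequal-variance t-test for the main question 3 comparison, and name Welch's test for the late-recurrence comparison too. For the latter, specify a studentized permutation p value if fewer than about 10 lesions qualify, because Welch is mildly liberal there at a Bonferroni level. Choosing 5 of 71 lesions can be done in about 13 million ways, so the p value is fine enough for an alpha of 0.0025. With unequal spread the permutation test is itself approximate, so a result from so few lesions should be read cautiously.

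The cost is one phrase in two places and one software option, with no added patients. At equal SDs, Welch gives up less than 1 point of power in the main comparison.
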